5 INTRODUCTION

5.1 Background

Vagus nerve stimulation (VNS) has an established history of reducing airway distress. VNS has at least two mechanisms of action that may profoundly affect respiratory function in patients with respiratory distress due to CoVID-19.

First, vagus nerve stimulation modulates bronchoconstriction¹⁻³, acute stimulation has demonstrated a marked improvement in Work of Breathing (WOB) as well as Forced Expiratory Volume (FEV₁) in patients with severe respiratory distress due to airway reactivity. This effect appears to occur via an afferent response to stimulation of the vagus nerve.

Second, and perhaps more importantly, VNS has been shown to be a potent moderator of pathologic immune reactions, specifically suppressing pro-inflammatory cytokine levels via activation of the Cholinergic Anti-inflammatory Pathway (CAP). VNS is currently being studied to modulate pro-inflammatory cytokine patterns and concentrations in a variety of acute and progressive inflammatory conditions, ranging from septic shock and asthma to stroke, rheumatoid arthritis and Inflammatory Bowel Disease.⁴⁻⁸ VNS has been studied in animal models of acute septic shock, consistently demonstrating life-saving potential. In one such study, cecal ligation and puncture was used to induce a septic state in an animal model. VNS reduced the expression of cytokines which was tightly associated with survival.⁹ Specifically, in animal and human models, this neuromodulatory therapy has the capacity to reduce the expression of inflammatory mediators, including TNF- α , IL-6 and IL-1 β . These are precisely the same cytokines which are elevated in ARDS and other inflammatory disorders. In all cases, the therapy has shown considerable promise as a potential alternative to steroids (having potent anti-inflammatory activity but without the adverse side effects of steroids) and biologic therapies targeting pro-inflammatory cytokines (broadly – e.g., tofacitinib, or specifically – e.g., adalimumab, etanercept, and infliximab).

Viral-induced acute respiratory distress syndrome (ARDS), including those caused by SARS CoV-1 and MERS are characterized by a massive systemic pro-inflammatory state. Although a pro-inflammatory environment is required to control the rate of infection as well as the eradication of infected and compromised cells, the massive response to these viruses, primarily due to leukocytes of the innate arm of the immune system, is part of the problem as a significant number of tissues are damaged and lost secondary to the infected tissues in a by-stander and collateral manner.¹⁰⁻²⁸ A simple, drug-free approach to attenuate this systemic inflammation would be of significant benefit to the progression of the syndrome and potentially improve the overall recovery of the patients.

For these reasons, we propose that VNS may ameliorate the over-activity of the pro-inflammatory immune condition in CoViD-19 patients, thus conferring a superior therapeutic option especially for elderly patients and those presenting with respiratory illness in setting of comorbid conditions who experience severe symptoms. These groups are at particularly high risk of requiring mechanical ventilation, developing ARDS, experiencing severe cytokine storm and have a higher mortality rate.

Non-Invasive Vagus Nerve Stimulation (nVNS)

Historically, VNS was delivered using implanted signal generators coupled to leads having electrodes that wrap around the vagus nerve. The vagus nerve is located within the carotid sheath, and thus the implantation surgery is complicated with inherent risks, particularly in the critically ill. More recently, a non-invasive approach to vagus nerve stimulation (nVNS) was cleared by the FDA for the acute treatment of pain associated episodic cluster and migraine headaches and the prevention of cluster headaches and migraine headaches. This device, gammaCore® (electroCore, Inc., Basking Ridge, NJ) is handheld and requires no surgery or implants. The device is applied by healthcare providers or patients to the skin at the neck over the vagus nerve to deliver periodic treatments of VNS non-invasively.

An Emergency Use Application for use of VNS in CoViD-19 patients was granted by the FDA on July 10, 2020.

With respect to bronchoconstriction, early studies demonstrated modulation of airway reactivity in hospitalized asthmatic patients, improving various measures of airway patency.^{2,29}

Non-invasive VNS (nVNS) is a safe method of stimulating the vagus nerve, with minimal side effects. It does not require surgery or an invasive procedure that would otherwise limit its utility in the critically ill. The stimulation can be either self-administered or administered by a health care practitioner. There are numerous studies with both implanted and nVNS in multiple animal models and humans that have demonstrated a modulation of the inflammatory cascade with an improvement in survival.

gammaCore® (nVNS) has been studied in approximately 2,000 patients as part of clinical trials with an excellent safety profile. It is available through commercial insurers and the private pay market, and is listed on the federal supply schedule available for purchase by the VA and Department of Defense and also carries a CE mark for distribution abroad. More than ten thousand patients have been successfully treated in the United States and abroad.

CoViD-19 Respiratory Issues Involve Virally-triggered Severe (Lethal) Cytokine Expression

COVID-19 (coronavirus disease 2019) is caused by SARS CoV-2 (severe acute respiratory syndrome coronavirus 2) and is related to the coronavirus which caused SARS in 2003 (SARS CoV-1). The virus is transmitted either through airborne droplets (e.g. coughing or sneezing) or direct contact (e.g. through a surface containing the virus), with a mean incubation period between 4 and 7 days (range 2 days to > 2 weeks). As of April 3, 2020, there are over a million confirmed cases and rising with 55,000 individuals deceased to date. This gives a current mortality rate of 5.3 %, although the base case of confirmed cases may be markedly underestimated. Elderly and those with comorbid conditions including heart disease, diabetes, and asthma seem to have a higher mortality rate.

Many CoViD-19 patients experience moderate to severe respiratory symptoms, including shortness of breath and impaired oxygen saturation. Eighty-eight percent (88%) of patients present with respiratory symptoms. A significant and increasing number of CoViD-19 patients require hospitalization, and progress to being intubated and/or ventilator dependent. Given the

rapid spread of this contagion, concern exists that the international healthcare systems do not have the number of ventilators and/or ICU beds to meet the expected demand in the coming months.

The most critically afflicted can experience pneumonia and/or ARDS. Accumulating evidence suggests that this subgroup with severe CoViD-19 likely have a cytokine storm syndrome, a hallmark of ARDS that includes dramatic increase in the expression of pro-inflammatory cytokines, mainly TNF- α , IL-6 and IL-1 β among others. Elevations in IL-6 seem to be a particularly poor outcome indicator of respiratory compromise. It is believed that the mortality of ARDS is at least partially the result of an over activity of the patient's immune system.³⁰ Predictors of fatality from a recent retrospective, multicentre study of 150 confirmed CoViD-19 cases in Wuhan, China, included elevated ferritin (mean 1297.6 ng/ml in non-survivors vs 614.0 ng/ml in survivors; $p<0.001$) and IL-6 ($p<0.0001$)³¹, suggesting that mortality and respiratory decompensation may be due to virally driven hyperinflammation.

Therapies that could block the cytokine storm may help improve survival and decrease the need for ventilator use and prolonged respiratory support. Other companies are in fact developing pharmaceutical approaches for the treatment of cytokine storm³², or plasma infusions from those who have recovered from the virus. At this point there is no cure or vaccine for the virus and neither is there a treatment approach to dampen the systemic inflammation.

Proposal to Use gammaCore® nVNS to Reduce Severe Respiratory Disease Associated with CoViD-19

Given the CE mark and excellent safety profile, including the twenty year history of the use of VNS to block the over production of pro-inflammatory mediators via the CAP (cholinergic anti-inflammatory pathway), and the lack of other effective or reasonable options during this pandemic we propose deploying gammaCore® (nVNS) devices for prophylactic use to those who have been diagnosed as infected with the virus, but before the cytokine storm begins to cause and/or exacerbate the severe respiratory distress syndrome. The hypothesis is that the administration of non-invasive VNS using gammaCore®, during and following severe infection with CoViD-19 may prevent the worsening inflammatory response and acute injury associated, thus decreasing ventilator dependence and mortality of the virus. If utilized early enough in the course of disease we hope to reduce ventilator dependence and improve survival with a scientifically driven safe and cost-effective approach. Furthermore, through additional acute utility of gammaCore® (nVNS) in cases of ARDS and cytokine storm we aspire to effectively blunt the pro inflammatory response, reduce mortality and liberate patients from mechanical ventilation earlier which will assist in deploying the ventilator to other patients in need during the CoViD-19 pandemic.

electroCore has designed a non-invasive vagus nerve stimulation (nVNS) device called gammaCore®. The gammaCore® (nVNS) device is a handheld, battery-powered unit that produces a proprietary electrical waveform in the vicinity of the vagus nerve in the neck. Each dose (or stimulation) is relatively brief (120 seconds) and the user maintains control over the stimulation intensity.

gammaCore® is currently commercially available for the treatment of cluster and migraine headaches, and broad safety data with thousands of patients treated in the US Europe and the UK in both clinical trials and routine clinical care.

Treatment paradigms have been developed and tested in clinical trials to support FDA clearance for the acute treatment of pain associated with episodic cluster and migraine headaches, and the prevention of cluster and migraine headache. This experience demonstrates that nVNS may be administered safely in up to 24 two-minute doses (stimulations) per day. We thus have data to draw on as to how to effectively stimulate the vagus nerve. Given the multiple modes of action with blocking the CAP, and acute bronchodilatation, using a similar treatment paradigm for a trial to evaluate nVNS treatment of ARDS is reasonable. The device should be used both prophylactically and acutely early in the course of the disease prior to mechanical ventilation, and once trained, treatment can be fully managed by either a healthcare professional or the patient. If one waits until mechanical ventilation has started, it is less likely that a therapy will be able to block the cytokine storm and outcomes will be less profound.

With respect to the theoretical cardiac and respiratory side effects of non-invasive treatment, historically, stimulation of the vagus nerve is associated with adverse side effects, including bradycardia and bronchoconstriction. These effects were shown to be the result of indiscriminant stimulation of all fibers in the vagal bundle (the vagus nerve is primarily comprised of A and C fibers), which could be avoided by specifically tuning the electrical signals to selectively stimulate only the A fibers. This is possible because of the difference in electric field strengths necessary to activate the different fiber types.³⁴

The intensity, pulse duration and frequency of gammaCore® (nVNS) stimulation parameters have been optimized to induce signals in the large, myelinated A β fibers of the cervical branch of the vagus nerve. Since gammaCore® activates only the low threshold afferent A β fibers, versus the high threshold efferent C-fibers that innervate the heart, there is no known risk for adverse cardiac or other systemic parasympathetic effects.

electroCore has conducted pre-clinical studies to assess the potential risk of vagus nerve overstimulation on the heart and airways. Several studies were conducted in beagle dogs with hypersensitized airways (worst case for airway reactivity) at maximum stimulation output for 2 minutes. Review of heart rate and airway resistance before, during and after stimulation indicated that there were no significant adverse changes associated with stimulation.³⁷ These results are consistent with the human clinical experience with the gammaCore® device. Regarding the theorized mechanism of action, afferent fibers from the vagus nerve enter the brain and synapse onto the nucleus tractus solitarius (NTS) in the brain stem¹, making connections with many structures in the brain including the locus coeruleus (LC), the periaqueductal gray (PAG) and the raphe nucleus (RN).³⁵ These structures are known to control the release of key inhibitory neurotransmitters. Numerous animal and clinical studies over the last 25 years have implicated the activity of these structures, in particular the LC, in the mechanism of action of VNS to inhibit seizures.³⁶

Clinical Use for Clinical Care

Given the lack of other effective and/or reasonable options for a patient with CoViD-19 respiratory distress and the anticipated demands on our healthcare system, considering gammaCore® (nVNS) therapy, we propose, is a reasonable approach. To achieve goal of decreasing health care burden with patient benefit of decreasing ventilator dependency, inflammatory response and mortality, plan to use it early in course of disease i.e. prior to severe respiratory distress and the need for mechanical ventilation.

The presumptive mechanisms of bronchodilatation and modulation of the cytokine storm would suggest that early intervention is ideal in improving pulmonary function and avoiding respiratory depression.

- 1) Prevention. Mitigation of pro-inflammatory immunokine release would be best achieved with two doses (stimulations), consisting of a two-minute stimulation, on each side of the neck three times a day (am, afternoon and an hour before bed). This would be a total of 6 treatments (2 stimulations x 3 times per day) of stimulation as a prophylactic/preventive measure. This dosage is well below the known safety dosage threshold.
- 2) In addition, patients may receive additional treatments when experiencing acute respiratory distress. Similarly, one treatment is two doses (stimulations). Each treatment (consisting of two-minute stimulation on each side) is performed on the neck. If shortness of breath (SOB) persists 20 minutes after start of first treatment, administer a second treatment. Maximum number of acute treatments per day is 9. This is symptomatic control and can be used to improve FEV₁, Work of Breathing or dyspnea.

6 CLINICAL INVESTIGATION OBJECTIVES

The aims of this study are to summarize and compare the incidence of clinical events and pro-inflammatory cytokine levels in patients randomized to use of gammaCore Sapphire plus standard of care vs standard of care alone in patients hospitalized for CoViD-19. In addition, this study is intended to demonstrate the safety of gammaCore Sapphire use in patients hospitalized for CoViD-19.

Specific clinical events to be summarized include, but are not limited to:

- Changes in oxygen support requirements (no oxygen support, low-flow oxygen support, nasal high-flow oxygen support, noninvasive mechanical ventilation, and invasive mechanical ventilation)
- Changes in O₂ saturation
- PaO₂/FiO₂ ratio
- Proportion of subjects requiring mechanical ventilation
- Days to onset of mechanical ventilation
- Live discharge from the hospital
- Patient length of stay
- Mortality
- Shortness of Breath
- Clinical improvement Scale

Specific laboratory measurements to be summarized include, but are not limited to:

[figure not shown]
- TNF- α
- IL-1 β
- IL-6
- CRP
- Ferritin
- D Dimer
- Pro-Calcitonin

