 - Total number of gammaCore® treatments administered with Date/time
- Daily Tx Log
 - Oxygen Requirements, Oxygen level (%), Ventilator Dependence, Date and time of Ventilation, Patient discharge home, (if applicable) Date and time of Discharge, Survival
- Clinical Improvement Ordinal Scale
- Concomitant medication and adverse event assessments

All Odd Days Starting Day 5

Same as Days 1 and 3

Study Completion

The last day of the study will be determined by discharge, transition to mechanical ventilation and/or if the patient is unable to continue i.e. death or feasibility impossible. The following will be recorded:

- Study Measurements:
 - Height/Wt, BMI, Temperature, Blood Pressure, O₂ Saturation, PaO₂/FiO₂ ratio, Shortness of Breath, Cough
- Labs (Standard of care)
 - Pro-Calcitonin, C-reactive protein, Ferritin, D-Dimer, CBC with differential,

Comprehensive metabolic panel

- Labs (Research) Early am blood draw (before 10 am)
 - TNF- α , IL-1 β , IL-6
- VNS stimulations
 - Total number of gammaCore® treatments administered, dates/times
- Daily Tx Log
 - Oxygen Required, Oxygen level (%) based on device type (HFNC / NC / Bipap / Optiflow), Ventilator Dependence (Yes / No), Date and time of Ventilation, Patient discharge home (Yes / No), Date and time (in 24 hour format) of Discharge, Survival (Yes / No) with Date and Time of Death
- Clinical Improvement Ordinal Scale
 - Concomitant medication and adverse events assessment

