7.2.1.5 Day of Study Completion

The last day of the study will be determined by discharge, transition to mechanical ventilation and/or if the patient is unable to continue. The following will be recorded:

- Study Measurements
 - Height/Wt, BMI
 - Temperature
 - Blood Pressure
 - O₂ Saturation
 - PaO₂/FiO₂ ratio
 - Shortness of Breath (Yes / No)
 - Cough (Yes / No)
- Labs
 - Pro-Calcitonin
 - C-reactive protein

Clinical Investigation Plan

- Ferritin
- D Dimer
- CBC with differential
- Comprehensive metabolic panel
- nVNS stimulations
 - Total number of gammaCore® treatments administered
 - Date and time of stimulations
- Daily Tx Log
 - Oxygen Required (Yes / No)
 - Oxygen level (%) based on device type (HFNC / NC / Bipap / Optiflow)
 - Ventilator Dependence (Yes / No)
 - Date and time of Ventilation
 - Patient discharge home (Yes / No)
 - Date and time (in 24 hour format) of Discharge
 - Survival (Yes / No) with Date and Time of Death
- Clinical Improvement Scale
 - Concomitant medication assessment
 - Adverse event assessment

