7.10.1.2 Summary Statistics

Data will be presented using summary statistics. For example, categorical data may be presented as proportions and counts; continuous data may be presented with the mean, median, minimum, maximum, and/or standard deviations. Kaplan-Meier methodology may be used to present time to event data. All comparisons between active and control groups are nominal in nature; confidence intervals and p-values may be presented, but are not intended for inferential purposes.

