7.10.1.3 Analysis of Objectives

Full details will be described in the Statistical Analysis Plan (SAP).

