7.10.4 Interim Analysis

An analysis of safety and feasibility was conducted on the first 20 patients who completed the hospitalization period. Only minor protocol deviations were noted with one SAE unrelated to device use. Neither incidence was a reportable event to the IRB.

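### Days to onset of mechanical ventilation is listed for comparison between arms with no time origin and no rule for patients discharged or dying unventilated, and either summary the plan permits can mislead

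*Combined protocol and SAP*

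**What the plan says.** The aim is to summarise and compare clinical events between arms. The Synopsis, section 6 and section 7.7.2 carry the same list, in which "Proportion of subjects requiring mechanical ventilation" is followed by a separate item, "Days to onset of mechanical ventilation". The second item is a name only. No section says from when the days are counted or what value an unventilated patient takes.

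Observation stops early by design. Section 7.2.1.5 states: "The last day of the study will be determined by discharge, transition to mechanical ventilation and/or if the patient is unable to continue". The Synopsis adds death to the last of these: "if the patient is unable to continue i.e. death or feasibility impossible".

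On method, section 7.10.1.2 says that "continuous data may be presented with the mean, median, minimum, maximum, and/or standard deviations", and the next sentence says that "Kaplan-Meier methodology may be used to present time to event data". Section 7.10.3 repeats both. The same sections call all between-arm comparisons nominal. Section 7.10.1.3 leaves the analysis of objectives to a statistical analysis plan, and the supplied text contains no further detail. Section 7.10.2 deals with outliers, withdrawals and partial data, but not with discharge or death before ventilation.

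**The concern.** A patient who goes home unventilated never acquires a number of days to ventilation. If the outcome is treated as a continuous number of days, only ventilated patients contribute. Being ventilated is a post-randomisation event that the device is meant to prevent (sections 5.1 and 7.6), so the two ventilated groups are not comparable even under perfect randomisation. Suppose the device prevents slow, late declines. The intubations left in its arm are then the early ones, and a real benefit reads as faster deterioration.

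If the outcome is instead treated as time-to-event with discharge as ordinary censoring, Kaplan-Meier assumes that discharged patients keep the same ventilation risk as those still in hospital. They are discharged because they recovered, so the curve overstates risk. The plan names both methods, chooses neither, and has no rule that guards against either problem.

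**Working it through.** The plan gives no ventilation rate, effect size or event count, so there is no figure of its own to reproduce. The only document input below is 30 patients per arm (section 7.4.1). Every rate and timing is an assumption.

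**1. How many patients would have a value**

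With ventilation risk p in both arms and n = 30, the expected number per arm is 30p. For one arm, P(0 or 1) = (1−p)^30 + 30p(1−p)^29 = q. The chance that at least one arm has 0 or 1 is 1 − (1−q)².

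| p | Expected per arm | q | At least one arm with 0 or 1 |
|---|---|---|---|
| 5% | 1.5 | 0.554 | 80% |
| 10% | 3.0 | 0.184 | 33% |
| 20% | 6.0 | 0.011 | 2% |

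An arm with 0 or 1 value has no standard deviation. Whether this is likely depends entirely on a rate the documents do not give.

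**2. Mean days among the ventilated**

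Assume control intubations fall evenly on days 1 to 12. Days 1–6 have mean 3.5, days 7–12 have mean 9.5, and the overall mean is 6.5. Take 6 early and 6 late control intubations as the unit.

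| What the device does | Mean days, device arm | Change in number ventilated | How the mean reads against 6.5 |
|---|---|---|---|
| Prevents all late ones | 3.5 | −50% | much earlier |
| Prevents half of late ones | (6×3.5 + 3×9.5)/9 = 5.5 | −25% | earlier |
| Prevents half, whatever the timing | 6.5 | −50% | no difference |
| Prevents half of early ones | (3×3.5 + 6×9.5)/9 = 7.5 | −25% | later |
| Prevents none, delays each by 2 days | 8.5 | 0% | later |

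In the first four rows fewer patients are ventilated, yet the mean moves down, stays put or moves up. In the second and fourth rows the reduction is identical and the direction is opposite.

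A second assumed pattern behaves the same way. Let 10% of controls be ventilated early (mean day 2) and 10% late (mean day 7), giving a mean of (2 + 7)/2 = 4.5 days. If the device prevents all the late ones, ventilation falls from 20% to 10% and the mean falls to 2.0 days.

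**3. Kaplan-Meier censored at discharge**

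Keep days 1 to 12 for ventilation with total risk 30%, so 0.30/12 = 0.025 of all patients each day. Discharge the other 70% alive evenly over days 4 to 14, so 0.70/11 = 0.0636 each day. Kaplan-Meier multiplies 1 − 0.025/(fraction still at risk). Up to day 4 the product is 0.900. From day 5 the fraction at risk falls by 0.0886 a day, from 0.836 on day 5 to 0.216 on day 12, where the factor is 1 − 0.025/0.216 = 0.884. The final product is 0.559.

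- Control: 1 − Kaplan-Meier = 0.44; cumulative incidence with discharge competing = 0.30, the true proportion.
- Device arm with half of late intubations prevented: 0.30 against a true 0.225.

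Here Kaplan-Meier keeps the right direction but overstates the risk in both arms. Cumulative incidence gives the right direction and the right size. The ventilated-only mean in this scenario, 6.5 against 5.5 days, points the wrong way.

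**The case against.** The strongest reply is that the plan does name a method that keeps unventilated patients in the analysis. The Kaplan-Meier sentence directly follows the one on means and medians, and days to an event is naturally time-to-event data. This stands. A reader might infer that the arms will be compared only among ventilated patients, but no section says so. The text shows only that such a summary is not ruled out. Equally, the Kaplan-Meier option is permissive, is not attached to this outcome, and comes without a censoring or competing-event rule.

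A reader might also infer that the device would be expected to look worse. The working does not support that: reversal occurs when late intubations are prevented and not under the other patterns.

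A third tempting step is to read the first 20 patients in section 7.10.4 ("Only minor protocol deviations were noted with one SAE unrelated to device use") as meaning that at most one was ventilated. That requires every ventilation to have been recorded as a serious adverse event. The documents do not say this, and they treat transition to ventilation as a study-completion event. The ventilation rate must therefore be left open.

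Finally, the stakes are limited. This is one of ten listed clinical events, no primary efficacy outcome is named, comparisons are nominal, and the proportion ventilated is reported beside it. All of that stands and bears on importance. It does not supply the missing definition.

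**Conclusion.** The outcome is undefined for patients discharged or dying unventilated, and both summaries the plan permits have a known fault here. The direction of a ventilated-only mean or median reflects which intubations are prevented, so it cannot be read as benefit or harm; that conclusion needs no particular rate. Censoring at live discharge inflates the risk, by 0.14 in the control arm of the assumed example (0.44 − 0.30). Sparse data are a serious problem at 5% ventilated (80%), moderate at 10% (33%) and negligible at 20% (2%).

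The documents do not establish that a ventilated-only comparison is planned or that the result would favour control. The effect is on descriptive interpretation, since no formal inference is claimed. The definition should be settled before analysis, but nothing in the design has to change.

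**What to change.** In section 7.10.1.2 and in the statistical analysis plan:

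- State that arms will not be compared by mean or median days among ventilated patients. Give those days as a by-patient listing.
- Count time from randomisation and include all randomised patients.
- Compare timing as the cumulative incidence of ventilation during the index stay, tabulated as the proportion ventilated by fixed days such as 3, 7 and 14.
- Treat live discharge and death without ventilation as competing events, and show deaths as their own category.

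Ventilation, discharge and death dates and times are already recorded in the Daily Tx Log, so the cost is plan wording and one table. Two things are given up or left open: the simple mean-days comparison is lost, and ventilation after discharge is not captured, which is why the table should be labelled as covering the index stay.
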